4.5 INCLUSION AND EXCLUSION CRITERIA

A subject, who meets all of the inclusion criteria, and none of the exclusion criteria, is eligible to participate in this study.

All subjects enrolled in the clinical study (including those withdrawn from the clinical study or lost to follow-up) will be accounted for and documented, assigning an identification code linked to their names, alternative identification or contact information.

This log will be kept up to date throughout the clinical study by the principal investigator or his/her authorized designee. To ensure subject privacy and confidentiality of data this log must be maintained throughout the clinical study at the clinical site.

To participate in this clinical subject, the subject must meet all of the following inclusion criteria:

4.5.1 Inclusion Criteria

- Subject (and caregiver, if applicable) signed the approved Informed Consent;
- Subject is ≥ 18 and ≤ 74 years of age;
- Subject is bilaterally treated with deep brain stimulation (DBS) in the subthalamic nucleus (STN) using a constant voltage device (i.e. Soletra™, Itrel™, Kinetra™, ActivaPC™ or ActivaRC™ IPG) and is responding satisfactory to CV stimulation in the Investigators opinion;
- In the physician's opinion, the subject is a suitable candidate for an IPG replacement with different stimulation paradigm;
- Subject needs and/or requests an IPG replacement within 12 months after consent and the current IPG has at least 2.6 V output left (i.e. approx. 30% of full battery capacity) at the time of subject enrollment;
- PD symptom onset is no longer than 20 years;

Clinical Investigational Plan

- Subject has a Hoehn & Yahr score <IV (on stim);
- Subject with a normal cognitive function (MMSE ≥25);
- Subject is fluent speaker (as judged by the investigator) of the language spoken in the country where the investigational site is located.

Subjects are not eligible for clinical study participation if they meet any of the following exclusion criteria:

4.5.2 Exclusion Criteria

- IPG battery has less than 30% battery life at the time of consent;
- Need to replace or reposition the leads or extensions during the IPG replacement procedure;
- Subject had >10 recurrent falls experienced in the 3 months prior to consent;
- Subject is unwilling to change to a St Jude Medical Infinity™ or Brio™ DBS system for the IPG replacement;
- Subject is unable to attend the study visits.

4.6 SUBJECT POPULATION

4.6.1 Subject Screening

All subjects presenting at the investigational site can be screened by a member of the investigational team previously trained on the CIP and delegated to do so.

Subjects who do not meet the inclusion/exclusion criteria will not be eligible to participate in this study.

Subjects meeting the inclusion/exclusion criteria will be fully informed about the study and asked to participate in the study. In case the subject agrees, a duly signed and dated Patient Informed Consent will be obtained.

4.6.2 Point of Enrollment

Subjects are considered enrolled in the study from the moment the subject has provided written Patient Informed Consent.

4.7 INFORMED CONSENT PROCESS

4.7.1 General process

Prior to enrolling in the clinical study and conducting study-specific procedures, all subjects will be consented, as required by applicable regulations and the center's IRB/EC. Informed consent must be obtained from each subject, and in case they have a caregiver, also from the caregiver prior to any study related procedures. The consent form must be signed and dated by the subject, the caregiver (if applicable), and by the person obtaining the consent.

The principal investigator or his/her authorized designee will conduct the Informed Consent Process. This process will include a verbal discussion with the subject on all aspects of the clinical study relevant to the subject's decision to participate in the clinical study.

The subject (and the caregiver, if applicable) shall be provided with the informed consent form that is written in a language that is understandable to the subject (and the caregiver, if applicable) and has been approved by the center's IRB/EC. Failure to obtain informed consent from a

Clinical Investigational Plan

subject prior to study enrollment should be reported to St. Jude Medical within 5 working days and to the reviewing center's IRB/EC/ consistent with the center's IRB/EC reporting requirements.

5.0 DEVICE UNDER INVESTIGATION AND CONTROL/COMPARATORS

5.1 DEVICE DESCRIPTION

In this study, the commercial available Infinity™ IPG with compatible header, the Brio™ IPG and the pocket adapter that are compatible with the Medtronic® extensions will be used in this study.

The IPG connects to the implanted extensions, which connect to the leads implanted in the brain. The IPG delivers electrical pulses through the extensions and leads to electrodes at a selected target in the brain in order to provide therapeutic stimulation. Physicians use the clinician programmer to create and modify a program for a patient. Subjects use the patient controller to control their prescribed programs. The patient magnet can turn the IPG on and off if the physician enables this functionality.

The Infinity™ IPG is an electronic device designed to be connected to one or two extensions. It is powered by a hermetically sealed battery within a titanium case and uses microelectronic circuitry to generate constant current electrical stimulation. The IPG is conductive on all sides, which allows the IPG case (also called 'can') to be used as an anode for monopolar stimulation. The IPG communicates wirelessly with system programmers and controllers, and IPGs are available in small and large sizes to accommodate different power needs. The IPG can receive software upgrades after implantation to provide patients with additional features as approved by the respective regulatory agencies. The models to be used in this study contain a header that is designed to allow the IPG to connect to Medtronic® extensions and/or leads that meet the compatibility guidelines.

The clinician programmer Application is a software application running on an iPad which is used by a clinician to wirelessly connect to Infinity™ IPGs to establish or modify the stimulation settings for a subject.

The patient controller is an off-the-shelf touch screen device (iPod Touch) with a SJM designed mobile Application software. Subjects use the patient controller to control their prescribed programs.

Description of the devices and instructions for use can be found in the User's Manual.

The components of the Brio™ DBS IPG to be used in this study include Brio™ DBS rechargeable IPG, a Pocket Adaptor™, a trial stimulator, a clinician programmer and a patient controller.

Description of the devices and instructions for use can be found in the User's Manual.

5.2 DEVICE HANDLING AND STORAGE

Only regulatory approved and commercially available shelf-stock will be used within commercially approved indications for the investigation. No specific device traceability is required.

Clinical Investigational Plan

6.0 PROCEDURES

6.1 STUDY FLOW CHART

Figure 2: Flow Chart

6.2 PROCEDURES

The clinical study will be conducted in accordance with the CIP. All parties participating in the conduct of the clinical study will be qualified by education, training, or experience to perform their tasks and this training will be documented appropriately.

The clinical study will not commence until St. Jude Medical receives written approval from the IRB/EC and relevant regulatory authorities and all required documents have been collected from the site(s).

**Clinical Investigational Plan**

Table 1: List of all study specific activities/procedures

Procedure	Enrollment	Baseline	IPG replacement & Programming	3 M FU (+-30 days)	12 M FU (+-30 days)
IC signed (Subject & Caregiver**)	X				
Inclusion/Exclusion Criteria	X				
Demographics		X			
Medical History		X			
Medication Review		X		X	X
Health Economic Data		X			X
(S)ADEs			X**	X**	X**
Withdrawal		X**	X**	X**	
Subject's Preference				X	X
QUESTIONNAIRES					
UPDRS I,II,III,IV On Med On Stim		X		X	X
UPDRS Part III On Med Off Stim		X		X	X
Satisfaction of Therapy (Subject & Caregiver**)		X		X	X
PDQ-39		X		X	X
TESTS					
Speech Handicap Index		X		X	X
Gait:					
1. Tinetti					
2. Freezing of Gait		X		X	X
3. Berg Balance Scale					
PROGRAMMING					
Programming Settings		X*		X*	X*
Initial testing/programming			X		
SURGERY/IMPLANT					
Implant Information			X		
Unscheduled Visit: is defined as a follow up that is not explicitly requested by the protocol. Subjects may be asked to return to the clinic for unscheduled study visit. The following information will be recorded: Reason for visit, Action taken, Record program settings (when re-programming has been done).					

Clinical Investigational Plan

*Before the questionnaires and the tests, the program settings for the subject should be recorded. After the questionnaires and the tests, the program settings for the subject may be optimized. The evaluator will decide when the settings are optimum. This might take several sessions.

**If applicable

Informed Consent Procedure and Inclusion/Exclusion Criteria:

Subject's eligibility criteria and Informed consent Procedure is performed at the Enrollment visit.

Subject Demographics:

Subject's Age, Weight, Height and Gender; will be collected at the Baseline 1 visit.

Medical History:

Diagnosis, Subject's year of symptom onset, year of initial diagnosis, length of diagnosis, subject's impression of worst symptom, will be collected at the Baseline visit.

Medication:

Subject's current medications for the indication will be collected at the Baseline visit and at the 3 and 12 Month Follow- Up visit.

Subject Data:

- Subject's Preference will be collected at 3 and 12 Month Follow-Up visit.
- UPDRS I (Mentation, Behavior and Mood), UPDRS II (Activities of Daily Living), UPDRS III (Motor exam) and UPDRS IV (Complications of Therapy) total scores 'On Medication/On Stimulation' will be collected at Baseline visit, 3 and 12 Month Follow- Up visits;
- UPDRS III Motor exam 'On Medication/Off Stimulation' will be collected at Baseline visit, 3 and 12 Month Follow- Up visit;
- Parkinson's Disease Questionnaire PDQ-39 (Quality of Life) will be completed at Baseline, 3 and 12 Month Follow- Up visit;
- Speech Handicap Index (SHI) will be collected at Baseline, 3 and 12 Month Follow- Up visit;
- Freezing of Gait Questionnaire (FOGQ) will be completed at Baseline, 3 and 12 Month Follow - Up visit;
- Tinetti Test will be assessed at Baseline, 3 and 12 Month Follow- Up visit;
- Berg Balance Scale will be assessed at Baseline, 3 and 12 Month Follow-Up visit;
- Satisfaction of Therapy Questionnaire for the subject will be completed at Baseline, 3 and 12 Month Follow- Up visit.

Caregiver:

Satisfaction of Therapy Questionnaire for the caregiver will be completed at Baseline, 3 and 12 Month Follow- Up visit (if subject has a caregiver).

Health Economic data:

Health Economic data will be collected at Baseline and 12 Month Follow- Up visit.

Programming:

Stimulation settings will be collected at each visit.

Initial programming parameters and settings will be collected at the IPG Replacement visit.

The frequency, pulse width and # of contacts (monopolar/bipolar) of the stimulation should be kept constant between the constant voltage and the constant current stimulation.

Additional programming sessions may be required during the study to optimize the therapy,

Clinical Investigational Plan

Implant:

Implant data will be collected at the IPG Replacement visit.

Please find here below a summary description of the questionnaires and tests:

Speech Handicap Index (SHI):

The SHI is a validated questionnaire with 30 items on speech related problems in daily life.

The Unified Parkinson's Disease Rating Scale (UPDRS):

The UPDRS is a rating tool to follow the longitudinal course of Parkinson's disease. It is made up of the following sections: I) Mentation (mental status), Behavior, and Mood, II) Activities of Daily Living (ADL), III) Motor Examination and IV) Complications of Therapy, which are evaluated by interviewing the patient. All responses are rated on a 0 to 4-point scale where 0 indicates 'none' and 4 indicates 'severe' symptom.

Freezing of Gait Questionnaire (FOGQ):

The FOGQ is a validated questionnaire with the purpose of identifying the freezing of gait.

Tinetti Test:

A measurement of functional ability that incorporates observation of performance of 13 activities with a focus on gait and balance. The activities include sitting, rising from a chair, standing, turning, reaching up, and bending down. The rating scale is normal, adaptive, or abnormal and is often used to assess the risk of falling.

Berg Balance Scale (BBS):

The test comprises a set of 14 simple balance related tasks, ranging from standing up from a sitting position, to standing on one foot. The degree of success in achieving each task is given a score of zero (unable) to four (independent), and the final measure is the sum of all of the scores

Parkinson's Disease Questionnaire (PDQ-39):

A disease specific instrument designed to measure aspects of health that are relevant to subjects with PD, and which may not be included in general health status questionnaires. The PDQ-39 is a self-administered questionnaire, which comprises 39 questions addressing eight dimensions of health that subjects consider to be adversely affected by the disease.

Satisfaction of Therapy Questionnaire:

Subject and caregiver (if applicable) will be asked to subjectively assess the rate of satisfaction with the deep brain stimulation therapy by completing a questionnaire.

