6.4 BASELINE VISIT

The following information will be collected at the Baseline visit.

Baseline visit can be combined with Enrollment visit.

The following data will be collected:

- Medication
- Health Economic Data
- Speech Handicap (SHI)
- Unified Parkinson's Disease Rating Scale 'On Med/On stim'. ("On" state is defined as approximately 30 minutes after a subject takes anti-Parkinson medication when both the clinician and the subject indicate that the medication dose is effective.)
- Unified Parkinson's Disease Rating Scale part III 'On Med/Off Stim'
- Freezing of Gait Questionnaire (FOGQ)
- Tinetti Test
- Berg Balance Scale (BBS)
- Parkinson's Disease Questionnaire (PDQ-39)
- Satisfaction of Therapy Questionnaire for the subject
- Satisfaction of Therapy Questionnaire for the caregiver, if applicable
- Record programming settings

Clinical Investigational Plan

- Adverse events or Withdrawal (if applicable)

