6.5 IPG REPLACEMENT VISIT & PROGRAMMING

The implanted Medtronic® IPG will be explanted and replaced by a SJM Infinity™ DBS IPG or a SJM Brio™ DBS system according to the standard surgical procedures and instructions for use. The time point for the replacement will be decided by the physician according to their standard procedure.

Intra-operative assessments and the initial CC programming session will be performed according to each individual site's standard procedure.

The frequency, pulse width and number of contacts (monopolar/bipolar) of the stimulation should be kept constant between the constant voltage and the constant current stimulation.

Additional programming sessions may be required to optimize the therapy.

The following data will be collected:

- Implant information
- Initial programming information
- Adverse Events or Withdrawal (if applicable)

6.6 3 MONTH FOLLOW UP VISIT (3 months +/- 30 days after IPG replacement)

The current programming settings will be recorded before the questionnaires and tests.

The following data will be collected:

- Subject's Preference
- Speech Handicap Index (SHI)
- Unified Parkinson's Disease Rating Scale 'On Med/On Stim' ("On" state is defined as approximately 30 minutes after a subject takes anti-Parkinson medication when both the clinician and the subject indicate that the medication dose is effective.)
- Unified Parkinson's Disease Rating Scale part III 'On Med/Off Stim'
- Freezing of Gait Questionnaire (FOGQ)
- Tinetti Test
- Berg Balance Scale (BBS)
- Parkinson's Disease Questionnaire (PDQ-39)
- Satisfaction of Therapy Questionnaire for the subject
- Satisfaction of Therapy Questionnaire for the caregiver, if applicable
- Medication
- Adverse events or Withdrawal (if applicable)

After the questionnaires and the tests, the SJM Infinity™ or Brio™ DBS system parameters shall be optimized if needed. The optimized settings will be recorded.

6.7 12 MONTH FOLLOW UP VISIT (12 months +/- 30 days after IPG replacement)

This visit will also serve as the end-of-study assessment.

The current programming settings will be recorded before the questionnaires and tests.

Clinical Investigational Plan

The following data will be collected:

- Subject's Preference
- Unified Parkinson's Disease Rating Scale 'On Med/On Stim' ("On" state is defined as approximately 30 minutes after a subject takes anti-Parkinson medication when both the clinician and the subject indicate that the medication dose is effective.)

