6.8 UNSCHEDULED VISIT

An Unscheduled Visit is defined as a follow up that is not explicitly requested by the protocol. Subjects may be asked to return to the clinic for unscheduled study visit.

The following information will be recorded:

- Reason for visit
- Action taken
- Record program settings (when re-programming has been done)

No specific assessment is required for this visit. If applicable, the AE or Withdrawal will be documented.

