12.1.3 Descriptive Endpoints

The following descriptive endpoints will be reported:

- The change in Speech Handicap Index at 3 and 12 Months compared to Baseline;
- The change in total UPDRS score and the individual UPDRS components at 3 and 12 Months compared to Baseline;
- The change in Levodopa medication at 3 and 12 Months compared to Baseline;
- The change in FOGQ scores at 3 and 12 Months compared to Baseline;
- The change in Tinetti Test scores at 3 and 12 Months compared to Baseline;
- The change in Berg Balance Scale scores at 3 and 12 Months compared to Baseline;
- The change in PDQ-39 Quality of Life scores 3 and 12 Months compared to Baseline;
- Proportion of subjects who indicate satisfaction with constant current at 3 and 12 Months;
- Proportion of caregivers who indicate satisfaction with constant current at 3 and 12 Months;
- Proportion of subjects who indicate preference on constant current over constant voltage at the 12 Month follow-up visit.
- Summary of Health Economic Data for constant current compared to constant voltage.

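### Constant-voltage settings may be changed after the Baseline tests without repeating the scores, so the descriptive change scores can compare superseded CV settings with optimised constant current

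*Combined protocol and SAP*

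**What the plan says.** In Table 1 (section 6.2) the row "Programming Settings" carries an asterisk at Baseline, 3 months and 12 months. The footnote gives the sequence. First, "Before the questionnaires and the tests, the program settings for the subject should be recorded". Then, "After the questionnaires and the tests, the program settings for the subject may be optimized". On duration it adds: "The evaluator will decide when the settings are optimum. This might take several sessions".

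The visit sections are not uniform. Section 6.4 (Baseline) lists "Record programming settings" and says nothing about optimisation. Section 6.6 (3 months) provides for optimisation of the new system after the tests and adds "The optimized settings will be recorded". Section 6.5 (replacement) collects implant and initial programming information. It asks that frequency, pulse width and number of contacts stay the same across the switch, and it allows further sessions afterwards.

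Two other places bear on recording. Section 6.2, under Programming, has stimulation settings collected at every visit. Section 6.8 has settings recorded at an unscheduled visit where reprogramming took place, but requires no assessment there.

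Section 12.1.3 lists the descriptive endpoints that are referenced to Baseline, for example "The change in Speech Handicap Index at 3 and 12 Months compared to Baseline". Section 12.4 plans no subgroup analyses.

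**The concern.** A change from Baseline is informative about CC only if the Baseline score describes the CV therapy that the subject leaves. The footnote allows the opposite order: score CV, then improve CV, then replace. Section 4.5.1 asks for a replacement within 12 months of consent, and 6.4 lets Baseline coincide with Enrollment, so there can be ample time for several CV sessions in between.

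CC is treated differently. It may be optimised after replacement and before the 3-month scores, and again before the 12-month scores. For a subject whose CV settings were improved after Baseline, part of the reported change may already have been present under CV. This is a single-arm before-and-after study with no concurrent CV group, so no other comparison would expose that part.

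What is at stake is the symptom evidence: SHI, UPDRS, FOGQ, Tinetti, Berg and PDQ-39.

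**Working it through.** The plan gives no figure on this point to reproduce: no rate of CV reprogramming, no expected gain and no SD of any change score. The check is therefore mainly a side-by-side reading.

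**1. Order of programming and scoring**

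| | Baseline (CV) | 3 months (CC) |
|---|---|---|
| Programming sessions foreseen before the scores | None stated; satisfactory response to CV required (4.5.1) | Yes, as needed after replacement (6.5) |
| Settings recorded before the tests | Yes (footnote) | Yes (footnote, 6.6) |
| Optimisation allowed after the tests | Yes (footnote); 6.4 silent | Yes (footnote, 6.6) |
| Changed settings recorded | No explicit line in 6.4 | Yes (6.6) |
| Scores taken again on the changed settings | No | Yes, at 12 months |

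The last row matters most. CC settings changed after the 3-month tests are still scored at 12 months. CV settings changed after the Baseline tests are never scored.

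**2. What can be recovered**

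- CV sessions on later days appear to be unscheduled visits, so 6.8 captures the settings.
- Frequency, pulse width and number of contacts should be unchanged across the switch, and the initial CC programming is recorded (6.5). Comparing these with the Baseline record would reveal most CV changes in those parameters. The text does not say, however, whether the tested or the later CV settings are the ones to keep.
- What remains is a change made on the Baseline day itself, mainly of amplitude. The each-visit rule in 6.2 could be met by the pre-test record alone.

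Recovering the settings does not recover the scores.

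**3. Which endpoints use a Baseline score**

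- Primary (4.4.1): preference at 3 months. No Baseline score.
- Secondary (12.1.2): procedure-related safety events after replacement. No Baseline score.
- Descriptive (12.1.3): the listed changes do use one.

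**4. Size**

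For each subject:

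CC score − tested CV score = (CC score − CV score at explant) + (CV score at explant − tested CV score)

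The first term is the contrast of interest. The second is the CV programming gain. If CC performs exactly as the CV therapy left behind, the mean change equals the second term alone:

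bias = q × g

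Here q is the share of subjects reprogrammed after the Baseline tests and g is their mean gain. Both are assumptions. I express g in SDs of the change score because the scales differ in range and direction. For a sense of scale I take n = 115, the target for the primary analysis (12.2); the plan states no number for the descriptive endpoints. Then bias in standard errors = q × g × √115 = q × g × 10.72, and the chance that a 95% interval excludes zero is Φ(b − 1.96) + Φ(−b − 1.96), where b is the bias in standard errors.

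| q | g (SD) | Bias (SD) | b | Interval excludes zero |
|---|---|---|---|---|
| 0 | any | 0 | 0 | 5.0% |
| 0.25 | 0.1 | 0.025 | 0.27 | 5.8% |
| 0.50 | 0.3 | 0.15 | 1.61 | 36% |
| 1.00 | 0.3 | 0.30 | 3.22 | 90% |

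The range runs from nothing to decisive, and the documents contain nothing that narrows it. The last row is an extreme, not an expectation.

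**The case against.** The strongest reply has four parts.

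- **The permission is generic.** One footnote serves three visits, it says that settings may be optimised, and the visit-level text describes optimisation after the tests only at 3 months and only for the new system. Subjects must also already respond satisfactorily to CV. This stands: routine CV reprogramming after Baseline is permitted, not shown. A satisfactory response is still not the same as optimised settings.
- **The data are not blind to it.** A reader might infer that affected subjects cannot be identified. The documents do not support that: 6.2 and 6.8 make most later changes recoverable. The case report forms are held separately, so whether they capture a change made on the Baseline day cannot be checked.
- **No primary or secondary inference is touched.** A reader might extend the point to the preference result. That would be wrong, since preference uses no Baseline score. Better CV before the switch would improve the remembered comparator and, if anything, work against CC. The affected endpoints are descriptive, and the visible text attaches no test or success criterion to them.
- **The remedy is partial.** If CV was sub-optimal at Baseline and never touched, later CC sessions could correct it and the gain would still appear under CC. A subset with unchanged CV settings leaves that in place and is selected on an event after Baseline. This stands too, and limits how the subset may be described.

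**Conclusion.** The point holds for the descriptive change-from-Baseline endpoints only. As written, the plan allows CV settings to be replaced after the Baseline scores and does not score the new settings. For those subjects the change compares superseded CV settings with optimised CC, and a CV gain carried over the switch is counted as change under CC.

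The size is unknown. It is zero if no CV settings change after Baseline; otherwise it is the share reprogrammed times their mean gain, and the documents give neither. The illustrative range rests on assumed shares and gains, on n = 115, and on CC performing the same as CV at explant. It shows that the bias cannot be dismissed or asserted in advance.

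It would go too far to say that a CV gain is in fact being credited to CC. The text shows only that the test-then-optimise order permits it. This is a cheap improvement, not a threat to the main result.

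**What to change.** 1. **Reconcile the Table 1 footnote with 6.4.** Where CV optimisation is planned, schedule the Baseline questionnaires and tests after it. If CV settings are nevertheless changed after the tests, record the changed settings and the date, as 6.6 already does for optimised settings at 3 months.
2. **Add to 6.5** a record of the CV settings in use immediately before explant.
3. **Add to 12.1.3, with a matching exception in 12.4,** a count of subjects whose CV settings at explant differ from those in use at the Baseline tests. Show each change-from-Baseline endpoint for all subjects and for those with unchanged CV settings, as a descriptive sensitivity display.

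The cost is one settings read-out and one extra table column, with no new test or visit. None of this restricts how the device is programmed. The unchanged subset should be labelled supportive only, because it is selected after Baseline and does not remove confounding from CC optimisation.
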